#### **PROTOCOL SYNOPSIS**

Title	An Open-Label Extension study of Inhaled Treprostinil in Subjects with Pulmonary Hypertension due to Parenchymal Lung Disease		
Study Phase	Phase II/III		
Indication	Pre-capillary pulmonary hypertension (PH) associated with interstitial lung disease (ILD) including combined pulmonary fibrosis and emphysema (CPFE)		
Primary Objective	To provide or continue to provide inhaled treprostinil for eligible subjects who participated in the RIN-PH-201 study		
Secondary Objectives	To evaluate the long-term safety and efficacy of inhaled treprostinil in subjects with PH associated with ILD including CPFE		
Efficacy Endpoints	Peak six-minute walk distance (6MWD)		
	
 
N-terminal pro-Brain Natriuretic Peptide (NT-proBNP)
 
		
	3. Quality of life as measured by the St. George's Respiratory Questionnaire (SGRQ)		
	4. Optional evaluation of change in biomarkers (specific targets to be determined) from Baseline to Week 48 (or study discontinuation if prior to Week 48)		
	5. Change in distance saturation product (DSP)		
Safety Endpoints	1. Adverse events (AEs)		
-	2. Oxygenation		
	a. Pulse oximetry (saturation of peripheral capillary oxygenation [SpO 2 ])		
	b. Supplemental oxygen requirement (L/min)		
	3. Pulmonary function:		
	
 
a. Forced expiratory volume in one second (FEV1)
 
		

	b. Forced vital capacity (FVC)		
	c. Total lung capacity (TLC)		
	d. Lung diffusion capacity (DLCO)		
	4. Clinical laboratory parameters		
	5. Vital signs		
	
 
Hospitalizations due to a cardiopulmonary indication
 
		
	7. Exacerbations of underlying lung disease; defined as an acute, clinically significant, respiratory deterioration characterized by evidence of new widespread alveolar abnormality		
Study Design	Multi-center, open-label study for eligible subjects who participated in RIN-PH-201.		
Sample Size	Approximately 266 subjects who completed protocol RIN-PH-201		
Summary of Subject	Inclusion criteria:		
Eligibility Criteria	
 
Subject voluntarily gives informed consent to participate in the study.
 
		
	2. The subject participated in study RIN-PH-201 and:		
	a. remained on study drug and completed all scheduled study visits or		
	b. permanently discontinued study drug during the RIN-PH-201 study due to clinical worsening and completed all remaining required scheduled study visits or		
	
 
c. was enrolled in study RIN-PH-201 at the time that the study/study subject was discontinued by the sponsor.
 
		
	3. Females of reproductive potential must be non- pregnant (as confirmed by a urine pregnancy test at Baseline) and non-lactating, and will:		
	
 
a. Either abstain from intercourse (when it is in line with their preferred and usual lifestyle), or
 
		

- b. Use two medically acceptable, highlyeffective forms of contraception for the duration of study, and at least 30 days after discontinuing study drug.
- 4. Males must use a condom for the duration of treatment and for at least 48 hours after discontinuing study drug.

#### Exclusion criteria:

- 1. The subject is pregnant or lactating.
- 2. The subject was prematurely discontinued from study RIN-PH-201 due to treatment related AEs.
- 3. The subject was prematurely discontinued from study RIN-PH-201 due to clinical worsening and did not undergo premature termination assessments prior to discontinuing study drug and/or did not complete all remaining study visits through the final scheduled visit.
- 4. The subject developed a concurrent illness or condition during the conduct of RIN-PH-201 which, in the opinion of the Investigator, would represent a risk to overall health if they enrolled in this study.

## **Drug Dosage** and Formulation

Inhaled treprostinil (6 mcg/breath)

#### Treatment phase:

All subjects will initiate inhaled treprostinil at a dose of 3 breaths (18 mcg) four times daily (during waking hours). Study drug doses should be maximized throughout the study, dose escalations (additional one breath four times daily) can occur up to every three days with a maximum dosing regimen of up to 15 breaths (90 mcg) four times daily, as clinically tolerated.

#### **Control Group**

None

## Route of Administration

Inhaled

#### **Procedures**

Subjects will be assessed at Baseline, Week 4, Week 12, and every 12 weeks thereafter through Week 108. Study visits will continue until each subject reaches Week 108 or until inhaled treprostinil become commercially available for patients with pre-capillary PH associated with ILD (whichever is sooner).

#### Key Assessments:

- Blood for NT-ProBNP will be obtained at Baseline, Week 48, and Week 108/study termination.
- Blood for clinical labs will be obtained at all scheduled study visits.
- A peak six minute walk test (6MWT) will be conducted at all scheduled study visits.
- Pulse oximetry will be performed immediately prior to, during, and immediately after each scheduled 6MWT.
- Pulmonary function tests (PFTs) will be conducted at Baseline, Week 12, Week 48, and Week 108/study termination.
- SGRQ will be conducted at Baseline, Week 48, and Week 108/study termination.
- Hospitalizations due to cardiopulmonary indications and exacerbations of underlying lung disease will be evaluated from the time of informed consent until study discontinuation.
- An optional blood sample will be collected for the analysis of biomarkers (specific targets to be determined) at Baseline and Week 48 (or study termination if prior to Week 48).

#### 1 BACKGROUND AND RATIONALE

#### 1.1 DEFINITION OF CLINICAL PROBLEM

Pulmonary hypertension (PH) is defined as an elevation in pulmonary arterial pressure and pulmonary vascular resistance. The World Health Organization (WHO) classifies PH due to lung diseases and/or hypoxemia as WHO Group 3 PH (Simonneau 2009). This classification includes PH due to interstitial lung disease (ILD) including combined pulmonary fibrosis and emphysema (CPFE).

Interstitial lung disease encompasses a heterogeneous group of parenchymal lung diseases that are characterized by significant scarring or fibrosis of the bronchioles and alveolar sacs within the lungs. Increased fibrotic tissue in ILD prevents oxygenation and free gas exchange between the pulmonary capillaries and alveolar sacs. The symptomatology of ILD is non-specific, and covers a wide range of symptoms, whose severity can vary substantially among patients. The incidence of PH in ILD has been reported in up to 86% of patients and is associated with a poorer prognosis and decreased quality of life (Nathan 2008, Nathan 2013).

Combined pulmonary fibrosis and emphysema characterized by emphysema, fibrosis, and abnormalities of gas exchange (Jankowich 2012). Up to 50% of CPFE patients have been reported to develop PH with increased pulmonary vascular resistance (PVR) associated with a decreased survival (Cottin 2010; Seeger 2013).

There are no approved treatments for PH in patients with ILD or CPFE; however, the results of some approved therapies for pulmonary arterial hypertension (PAH) have stimulated further investigation in these indications (Seeger 2013, Saggar 2014, Agarwal 2015, Roccia 2013).

#### 1.2 INHALED TREPROSTINIL BACKGROUND

#### 1.2.1 General Pharmacology

Treprostinil, 2-[[(1R,2R,3aS,9aS)-[[2,3,3a,4,9,9a-hexahydro-2-hydroxy-1-[(3S)-3-hydroxyoctyl]-1Hbenz[f]inden-5-yl]oxy]acetic acid, is a chemically stable tricyclic analogue of prostacyclin. The pharmacology of treprostinil is well-characterized and approved for the

treatment of PAH following either the subcutaneous (SC), intravenous (IV), inhaled (as treprostinil sodium), or oral (as treprostinil diolamine) routes of administration.

Prostacyclin is known to lower pulmonary artery pressure, increase cardiac output without affecting the heart rate, improve systemic oxygen transport and possibly reverse pulmonary arterial remodeling. There is increasing evidence that the ability to block the proliferation of pulmonary artery smooth muscle cells, along with vasodilation, may contribute to the therapeutic effects of prostacyclin in the treatment of PAH. Treprostinil acts by triggering direct vasodilation of the pulmonary and systemic arterial vascular beds and inhibition of platelet aggregation. *In vitro*, treprostinil induced concentration dependent relaxation of rabbit isolated pre-contracted mesenteric arteries and inhibited adenosine diphosphate induced platelet aggregation in human and rat platelet rich plasma. In animals, the vasodilatory effects of treprostinil reduce right and left ventricular afterload, thereby increasing cardiac output and stroke volume. The mechanism of action of treprostinil is therefore likely to be multifactorial.

Treprostinil for inhalation (Tyvaso®) is approved in the United States and Israel for the treatment of PAH (WHO Group I) in patients with New York Heart Association (NYHA) functional classification III symptoms, to increase exercise ability.

#### 1.2.2 General Toxicology

A well-defined clinical safety profile exists for treprostinil sodium; acute toxicity studies, repeat-dose toxicity studies, reproductive toxicity studies, and genotoxicity studies have been performed in both rats and dogs and support the chronic administration to patients (Remodulin® Package Insert 2014).

The toxicokinetic profile of treprostinil was also evaluated in acute and repeat dose toxicity studies of up to 13 weeks in duration in rodents and dogs which supported the chronic administration of inhaled treprostinil to patients. In addition, a two-year rat carcinogenicity study was performed with treprostinil inhalation at target doses up to 5.26, 10.6, and 34.1 mcg/kg/day which found no evidence for carcinogenic potential associated with inhaled treprostinil in rats at systemic exposure levels up to 35 times the clinical exposure at the target

maintenance dose of 54 mcg. Refer to the inhaled treprostinil Clinical Investigators Brochure for a full description of nonclinical data.

#### 1.2.3 Clinical Experience

A series of acute and chronic investigator-initiated clinical studies were conducted with inhaled treprostinil to optimize the formulation for inhalation, determine dose response, tolerability, and safety and also to evaluate safety and tolerability when combined with other PAH therapies (Channick 2006, Voswinckel 2006). In the acute dosing studies, administration of inhaled treprostinil resulted in pulmonary vasodilation at relatively low doses. In the chronic studies, administration of inhaled treprostinil resulted in sustained improvement of exercise capacity.

A randomized, double blind, placebo controlled, Phase III study (TRIUMPH-I) was conducted to assess the safety and efficacy of inhaled treprostinil in combination with approved PAH therapies. Two hundred and thirty-five subjects who were clinically stable on an approved background oral PAH therapy (bosentan or sildenafil) were randomly allocated to receive either placebo or inhaled treprostinil for 12 weeks. The primary efficacy endpoint was change in exercise capacity at Week 12 as measured by six-minute walk distance (6MWD). At Week 12, subjects receiving inhaled treprostinil had a median improvement of +21.6 meters in 6MWD and subjects in the placebo group had a median improvement of +3.0 meters. The Hodges-Lehmann placebo-corrected median change from baseline in peak 6MWD was +20.0 meters (p=0.00044). The durability of this result was supported by secondary measures related to the trough 6MWD, which was measured at least four hours after the last dose of inhaled treprostinil. At Week 12, trough 6MWD showed a placebocorrected median treatment effect of 13.7 meters (p=0.0066). The most commonly reported adverse events (AEs) in the inhaled treprostinil group were cough (54%), headache (41%), and nausea (19%). There were no remarkable treatment related changes in vital signs, physical examination findings, chest x-rays, pulmonary function tests, or clinical laboratory parameters (McLaughlin 2010).

An open-label, extension study of the TRIUMPH-I study to evaluate the use of long-term inhaled treprostinil therapy was also conducted (TRIUMPH-OL). Subjects received one to

12 breaths (6 to 72 mcg) four times daily to achieve daily doses of 24 to 288 mcg. The longest duration of inhaled treprostinil exposure in the open-label study was 5.4 years and the mean duration 2.3 years. There were observed improvements in median 6MWD at 6, 12, 18 and 24 months of 28, 31, 32 and 18 meters, respectively. These data support the durability of improvement in 6MWD obtained with inhaled treprostinil as demonstrated during the doubleblind phase of the study. Therapeutic benefit was also noted with improvements in the Borg dyspnea score, NYHA functional classification and quality of life (QOL). Survival was robust with one and two year Kaplan-Meier survival estimates of 97% and 91%, respectively, for subjects that remained in the trial. The most frequently reported AEs during the openlabel study were cough (39%), headache (31%), upper respiratory tract infection (22%), and nausea (22%). There were no clinically significant changes in clinical chemistry or hematology parameters. Unique findings that related to the inhaled route of administration, in addition to cough, were throat pain and throat irritation, occurring in 12% and 10% of subjects, respectively. These events were usually of mild or moderate severity and transient in duration. In a few subjects, these specific AEs were more pronounced as six subjects (3%) discontinued inhaled treprostinil due to cough, including one subject (<1%) with dry throat (Benza 2011).

## 1.3 RATIONALE FOR DEVELOPMENT OF STUDY DRUG IN DISEASE/CONDITION

Inhaled treprostinil has shown clinical improvements in exercise capacity after 12 weeks of therapy in patients with WHO Group I PH (McLaughlin 2010). Inhaled treprostinil is expected to directly target the more ventilated portion of the lungs in patients with WHO Group 3 PH minimizing the risk of ventilation perfusion mismatch and allowing for improvements in exercise capacity (Seeger 2013).

The use of inhaled prostacyclin therapy in patients with WHO Group 3 PH has been recently evaluated. In particular, Wang and colleagues (Wang 2015) reported data on 67 COPD patients with PH and found no change in arterial blood gases when a single dose of iloprost was administered during right heart catheterization (RHC). In addition, Bajwa and colleagues recently completed a prospective 16-Week study in nine COPD subjects with PH which

reported no notable changes in arterial blood gases over the 16-Week treatment period (Bajwa submitted). Finally, Agarwal and colleagues (Agarwal 2015) recently presented data on 35 patients with WHO Group 3 PH who received treatment with inhaled treprostinil for six months. This retrospective review reported a mean increase from baseline in 6MWD of 61 meters with obstructive and restrictive patients reporting mean increases of 71 meters and 50 meters, respectively. Notably, this study also found that inhaled treprostinil was well tolerated with cough being the most commonly reported AE. Data from these recently completed pilot studies suggest that inhaled treprostinil can be safely administered in patients with WHO Group 3 PH.

#### 1.4 CLINICAL HYPOTHESIS

This open-label study will evaluate the safety of continued therapy with inhaled treprostinil in subjects who have completed RIN-PH-201. This study hypothesizes that long-term safety findings will be similar to those observed in the randomized, placebo controlled study (RIN-PH-201).

#### **2 OBJECTIVES**

The primary objective of this study is to provide or continue to provide inhaled treprostinil for eligible subjects who participated in the RIN-PH-201 study.

Secondary objectives are to assess the long-term safety and efficacy of inhaled treprostinil in subjects with PH associated with ILD including CPFE.

#### 2.1 EFFICACY ENDPOINTS

To evaluate the effect of continued long-term therapy with inhaled treprostinil on the following:

- 1. Peak 6MWD
- 2. N-terminal pro-Brain Natriuretic Peptide (NT-proBNP)
- 3. Quality of life as measured by the St. George's Respiratory Questionnaire (SGRQ)
- 4. Optional evaluation of change in biomarkers (specific targets to be determined) from Baseline to Week 48 (or study discontinuation if prior to Week 48)
- 5. Change in distance saturation product (DSP)

#### 2.2 SAFETY ENDPOINTS

To evaluate the effect of continued long-term therapy with inhaled treprostinil on the following:

- 1. Adverse events (AEs)
- 2. Oxygenation
  - a. Pulse oximetry (saturation of peripheral capillary oxygenation [SpO2])
  - b. Supplemental oxygen (L/min) requirement
- 3. Pulmonary function:
  - a. Forced expiratory volume in one second (FEV1)
  - b. Forced vital capacity (FVC)
  - c. Total lung capacity (TLC)
  - d. Lung diffusion capacity (DLCO)
- 4. Clinical laboratory parameters
- 5. Vital signs
- 6. Hospitalizations due to a cardiopulmonary indication
- 7. Exacerbations of underlying lung disease; defined as an acute, clinically significant, respiratory deterioration characterized by evidence of new widespread alveolar abnormality.

#### 3 EXPERIMENTAL PLAN

#### 3.1 STUDY DESIGN

This is a multi-center, open-label study. Study visits will occur at Baseline, Weeks 4, 12, and every 12 weeks thereafter until Week 108. The study will continue until each subject has completed Week 108 or until inhaled treprostinil become commercially available for patients with pre-capillary PH associated with ILD including CPFE (whichever is sooner).

A schedule of study visits and assessments is presented in Section 3.2.

#### 3.2 OVERALL SCHEDULE OF TIMES AND EVENTS

Study Procedures	Baseline 	Treatment Phase			
Study Week		Week 4 	Week 12 	Follow-up Visits (every 12 weeks through study termination) 	Week 108 / Study Termination Visit
Informed Consent 	X				
Subject Eligibility 	X				
SGRQ 	X			X 	X
Physical Examination 	X				X
Vital Signs 	X	X	X	X	X
Clinical Laboratory Assessments 	X	X	X	X	X
N-terminal proBNP 	X			X 	X
Blood sample for biomarker evaluation (optional) 	X			X 	X 
Urine Pregnancy Test 	X	X	X	X	X
Peak 6MWT 	X	X	X	X	X
Pulse Oximetry 	X	X	X	X	X
Documentation of Supplemental Oxygen Requirement	X	X	X	X	X
PFTs 	X		X	X 	X
Dosing instructions / Dosing / Accountability	X	X	X	X	X
Telephone/Email Contact 		X	X	X	
Adverse Events 	X	X	X	X	X
Concomitant Medications	X	X	X	X	X
Hospitalizations 	X	X	X	X	X
Exacerbations of Underlying Lung Disease 	X	X	X	X	X

- NT-ProBNP: N-terminal brain natriuretic peptide; PFTs: pulmonary function tests; PH: pulmonary hypertension; SGRQ: St. George Respiratory Questionnaire; 6MWT: six-minute walk test
-  Baseline assessments (6MWT, pulse oximetry, PFTs, SGRQ, clinical laboratory assessments, NT-ProBNP, urine pregnancy test, optional biomarker sample [as applicable], vitals, and physical examination) for this study are those collected at the Study Termination Visit (Week 16) from study RIN-PH-201 and prior to initiation of open-label study drug. Informed consent and subject eligibility criteria are exclusive to this protocol.
-  The visit window for the Week 4 visit is ± 5 days; the visit window for all other visits is ± 14 days. Visits are scheduled based off of the day of first dose of study drug for the RIN-PH-202 study (i.e., four weeks after the first dose of study drug in this open-label study).
-  Vital signs must be collected after five minutes of rest (seated); no other measurements or procedures should be performed during this five minute period. When applicable, vital signs should be collected prior to the 6MWT. If vital signs cannot be obtained prior to the 6MWT then they should be obtained after recovery from the 6MWT. Vital signs measured will include blood pressure (systolic and diastolic), heart rate (HR), respiratory rate (RR), temperature, and weight.
-  Blood for NT-proBNP assessment must be drawn prior to conducting the 6MWT at Week 48 and Study Termination.
-  For subjects consenting to the optional biomarker sample. The optional biomarker sample must be drawn prior to conducting the 6MWT at Week 48 only or upon early termination if subjects discontinue the study prior to Week 48.
-  For females of childbearing potential.
-  The peak 6MWT must occur within 10 to 60 minutes after the most recent study drug dose. Prior to the start of each 6MWT the subject should rest (seated) for at least 10 minutes.
-  Pulse oximetry will be performed immediately prior to, during, and immediately after each 6MWT. Pulse oximetry will include the measurement of SpO2 and HR. The SpO2 and HR obtained immediately prior to and immediately following completion of the 6MWT will be recorded in the eCRF. In addition, the lowest recorded SpO2 (and corresponding HR) obtained during each 6MWT will be recorded in the eCRF.
-  PFTs will include the evaluation of FEV1, FVC, TLC, and DLCO. PFTs should be performed after recovering from the 6MWT.
- Telephone contact should occur at least weekly for the first 12 weeks of the study and at least monthly thereafter. Telephone contact may be replaced by a face-to-face interaction on the weeks where study visits occur and the information can be obtained during the visit. Subjects may be contacted via email in lieu of a telephone call. A copy of the emails and/or telephone contact sheets must be documented in the subject's source documentation. Email should not replace direct follow-up by phone or in clinic for clinically significant AEs or other emergent issues.
-  Any AEs that are ongoing at the Study Termination Visit from study RIN-PH-201 should be recorded as continuing AEs in this open-label study.
-  Any AEs that are ongoing at the Study Termination Visit for this protocol (RIN-PH-202) should be followed for up to 30 days after completion of the Study Termination Visit.
- During the follow-up assessments (scheduled every 12 weeks after Week 12), the SRGQ, PFTs, and NT-pre-BNP are only required at Week 48 and Week 108/Study Termination. For those subjects consenting to the optional biomarker sample, this sample is only required at Week 48 (or upon early termination if prior to Week 48).
-  Hospitalizations due to cardiopulmonary indications must be recorded in the eCRF from the time of informed consent until study termination. Adverse events resulting in hospitalizations, regardless of cause or duration, should also be recorded as SAEs per Appendix 15.2.
-  Exacerbations of underlying lung disease; defined as an acute, clinically significant, respiratory deterioration characterized by evidence of new widespread alveolar abnormality. Exacerbations will also be recorded as AEs.

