#### 3.3.2.6 Adverse Events

Any AEs that are ongoing at the Study Termination Visit for the RIN-PH-201 study should be recorded as continuing AEs in this open-label study.

Adverse events will be recorded throughout the course of the study from the time that each subject signs the ICF until the subject is either discontinued from the study or all Study Termination assessments have been completed. Each subject will be questioned for AEs at

each scheduled study visit and during required telephone/email contacts. Subjects will also be instructed to spontaneously report all AEs throughout the study.

All AEs should be followed until either resolution (or return to normal or Baseline values), until they are judged by the Investigator to no longer be clinically significant, or for at least 30 days if the AE extends beyond the final study visit. All AEs meeting the criteria for serious (*i.e.*, serious adverse events [SAEs]) should be followed until resolution, death, or the subject is lost to follow-up even if they are ongoing more than 30 days after completion of the final study visit (Study Termination). All AEs/SAEs that occur while the subject is on study drug will be recorded as instructed in this protocol.

Sections 9 and 15.2 provide the guidelines and definitions for recording AEs.

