#### 8 STUDY TERMINATION

#### 8.1 CRITERIA FOR SUBJECT WITHDRAWAL

A subject may voluntarily withdraw or be withdrawn from the study and/or study drug by the Investigator at any time for reasons including, but not limited to, the following:

- The subject wishes to withdraw from further participation.
- A serious or life-threatening AE occurs or the Investigator considers that it is necessary to discontinue study drug to protect the safety of the subject.
- The subject consistently deviated from the protocol.
- The subject's behavior is likely to undermine the validity of his/her results.
- The subject permanently initiates an infused prostacyclin therapy for >29 days.
- The subject becomes pregnant.

If a subject is discontinued from the study prematurely, the Investigator must provide an explanation in the eCRF and complete the End of Study Record for that subject. If study drug has been administered, the Investigator should make every effort to perform all scheduled evaluations prior to discharge. In the event that a subject discontinues study drug prematurely due to an AE, the subject will be followed until either the Investigator determines that the AE has resolved, it is no longer considered clinically significant, the subject is lost to further follow-up, or for 30 days if the AE extends beyond the final visit.

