#### 9.1.2 Serious Adverse Event

A serious adverse event (SAE) is an AE occurring at any time after informed consent that results in any of the following outcomes:

- Death
- A life-threatening AE
- Inpatient hospitalization or prolongation of existing hospitalization
- A persistent or significant disability/incapacity
- A congenital anomaly/birth defect
- Results in a medically important event of reaction

Life-threatening in this context refers to a reaction in which the subject was at risk of death at the time of the reaction; it does not refer to a reaction that hypothetically might have caused death if more severe.

Medical and scientific judgment should be exercised in deciding whether other situations should be considered serious reactions, such as important medical events that might not be immediately life threatening or result in death or hospitalization, but might jeopardize the subject or might require intervention to prevent one of the other outcomes listed above. Examples of such events are intensive treatment in an emergency room or at home for allergic bronchospasm, blood dyscrasias, or convulsions that do not result in hospitalization or development of dependency or abuse. Any suspected transmission via a medicinal product of an infectious agent is also considered a serious adverse reaction.

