#### 9.3 FOLLOW UP OF ADVERSE EVENTS

All AEs should be followed until either resolution (or return to normal or baseline values), until they are judged by the Investigator to no longer be clinically significant, or for at least 30 days if the AE extends beyond the final visit. All SAEs that occur during the study will be followed until resolution, death, or the subject is lost to follow-up even if they are ongoing more than four weeks after completion of the final study visit. Supplemental measurements and/or evaluations may be necessary to investigate fully the nature and/or causality of an AE or SAE. This may include additional laboratory tests, diagnostic procedures, or consultation with other healthcare professionals. The eCRF pages should be updated with any new or additional information as appropriate.

If, at any time, the subject withdraws from the study and/or changes from study drug to commercially available Tyvaso, any AEs/SAEs that occur on Tyvaso (including product use errors, product quality problems, and therapeutic failures) will be reported following local post-marketing reporting requirements, or Continued Access Plan local reporting requirements (see Section 3.3.2.11). These events will not be included in the protocol analysis.

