# 9.4 REPORTING RESPONSIBILITIES OF THE INVESTIGATOR All SAEs, regardless of expectedness or causality, must be reported to the Sponsor by fax/email ) within 24 hours of awareness.

A completed SAE Notification Report form along with any relevant hospital records and autopsy reports should be provided to Global Drug Safety at United Therapeutics Corporation. A follow-up SAE Notification Report form must be forwarded to Global Drug Safety at United Therapeutics Corporation within 24 hours of the receipt of any new or updated information. The Investigator must also promptly notify their Investigational Review Board (IRB) or Ethics Committee (EC) of the SAE, including any follow-up information, in accordance with applicable national regulations and guidelines set forth by the IRB or EC.

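### Schedule footnote 12 caps follow-up of any ongoing adverse event at 30 days, contradicting the protocol's own rules for serious and for other adverse events

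*Protocol*

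**What the plan says.** The Adverse Events row of the schedule (Protocol 3.2) carries footnotes 11 and 12. Footnote 11 deals with events carried over from the parent study. Footnote 12 sets how long follow-up lasts, counted from the final visit: "Any AEs that are ongoing at the Study Termination Visit for this protocol (RIN-PH-202) should be followed for up to 30 days after completion".

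The body of the protocol sets different rules:

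- **SAEs.** Section 9.3: "All SAEs that occur during the study will be followed until resolution, death, or the subject is lost to follow-up". Section 3.3.2.6 gives the same end states and says that the duty continues "even if they are ongoing more than 30 days after completion of the final study visit (Study Termination").
- **All AEs.** Section 3.3.2.6 ends follow-up at resolution, at the investigator's judgement that the event is no longer clinically significant, or "for at least 30 days if the AE extends beyond the final study visit". Section 9.3 has the same three alternatives.
- **AEs that lead to stopping study drug.** Section 8.1 lists resolution, loss of clinical significance and loss to follow-up, "or for 30 days if the AE extends beyond the final visit". It has no separate line for SAEs.

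Section 9.1.2 fixes how the terms relate: "A serious adverse event (SAE) is an AE occurring at any time after informed consent" that meets one of the listed outcomes.

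**The concern.** The schedule is the page that site staff are likely to use at the visit. Read alone, footnote 12 tells them that 30 days is the most that any open event needs. For an SAE that permits stopping before the outcome is known. For a non-serious event it permits stopping sooner than the body text allows.

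Long-term safety is a secondary objective of this extension study, and how an open SAE ends is part of that information. What is at stake is the care and documentation of individual subjects who leave the study with an unresolved event.

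**Working it through.** There is no sample size, power or event figure to reproduce, so the check compares the wordings.

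| Place | Events covered | When follow-up may end | Separate SAE rule |
|---|---|---|---|
| 3.2, footnote 12 | any AE open at the Study Termination Visit | 30 days is a maximum | no |
| 3.3.2.6 | all AEs | resolved, not clinically significant, or 30 days as a minimum | yes, no time limit |
| 9.3 | all AEs | same as 3.3.2.6 | yes, no time limit |
| 8.1 | AEs leading to drug discontinuation | resolved, not clinically significant, lost to follow-up, or 30 days | no |

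**Step 1: does footnote 12 reach SAEs?** It covers any AE, and Section 9.1.2 makes an SAE an AE. Footnote 14 of the same schedule does mention SAEs: "Adverse events resulting in hospitalizations, regardless of cause or duration, should also be recorded as SAEs per Appendix 15.2". That concerns recording, not duration. No schedule footnote gives an SAE exception to footnote 12, and footnote 12 does not refer to 3.3.2.6 or 9.3.

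**Step 2: an SAE still open on day 31 after the Study Termination Visit.** Under footnote 12, follow-up has ended. Under 3.3.2.6 and 9.3 it must continue. Both count from the final study visit, so the two rules cannot both be obeyed.

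**Step 3: a non-serious AE that is unresolved and still clinically significant.**

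- Stopped at day 10: allowed by footnote 12. It breaches 3.3.2.6, because none of its three end conditions is met.
- Followed to day 45: allowed by 3.3.2.6, but beyond the footnote's limit.
- Stopped at exactly day 30: satisfies both.

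A single value that meets both wordings does not reconcile them, since one is a ceiling and the other a floor.

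**Step 4: does another section close the gap for a site that relies on the schedule?** Section 9.4 requires a follow-up SAE report "within 24 hours of the receipt of any new or updated information". It has no 30-day limit, but it is triggered by information arriving and does not tell the site to keep seeking it. Section 8.1 names a serious or life-threatening AE as a reason for withdrawal, then offers a 30-day end point with no SAE exception. A site looking for confirmation of a 30-day stop could find it there.

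**The case against.** The strongest reply is that the protocol already answers the question. Two dedicated sections state the SAE rule in full, and 3.3.2.6 deals expressly with SAEs that run past 30 days after this same visit. Section 9.3 says SAEs *will* be followed, while footnote 12 says only *should*. The protocol also often names AEs and SAEs side by side, so a reader could take the footnote as shorthand for the general AE rule, with SAEs left to their own sentences. On that view, harm requires a site to use a table footnote and overlook both adverse event sections.

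Most of this stands, and it is why the point is minor: the intent is not in doubt. It does not make the footnote correct. The definition in 9.1.2 puts SAEs inside its wording. Even read as shorthand for the general AE rule, it turns a minimum into a maximum.

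A reader might also infer that deaths would be missed, or that SAE reporting to the sponsor stops at 30 days. The documents support neither. The death listing and summary in SAP 11.2 have their own 30-day rule, tied to the last dose for subjects who discontinued early, and do not refer to footnote 12. Section 9.4 sets no end date for reporting.

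**Conclusion.** The point holds as a minor inconsistency: footnote 12 is wrong as written, in two respects. It puts a limit on SAE follow-up where 3.3.2.6 and 9.3 have none, and it makes 30 days a ceiling for other AEs where those sections make it a floor.

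The conclusion rests on two readings: that an SAE is an AE, which 9.1.2 states, and that the footnote's limit is a maximum, which is its plain sense. The practical risk arises only where a site works from the schedule without the body sections.

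The size cannot be put in subjects or days. The documents do not say how many SAEs would be open at the Study Termination Visit or how long they would last. No effect on death counts or on any efficacy result is shown.

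**What to change.** Reword footnote 12 along these lines: *An AE still open at the Study Termination Visit is followed until it has resolved or is no longer clinically significant, or for a minimum of 30 days. An SAE is followed until it resolves, the subject dies or is lost to follow-up; see Section 9.3.* Add the same SAE cross-reference to the follow-up sentence in Section 8.1.

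The cost is wording in two places. Section 13.1 requires regulatory and ethics approval of amendments before they take effect, so the change is best carried in the next amendment. No visit or assessment is added. The only extra follow-up is what 3.3.2.6 and 9.3 already require, at sites that had been working from the footnote.
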